6.2 Investigational Medicinal Product

Ciclopirox (6-cyclohexyl-1-hydroxy-4-methyl-2(1H)-pyridone), often in the form of its olamine (2-aminoethanol) salt, is an off-patent synthetic antimicrobial agent which has previously been approved in the United States (US) as an anti-fungal topical treatment in the forms of gels, creams, lacquers and shampoos (anatomical therapeutic chemical [ATC] codes: D01AE14).

Ciclopirox olamine also acts as a pharmacological chaperone in CEP. By binding to UROIIIS, it stabilizes its structure and reduces its unfolding and degradation with time. Thus, ciclopirox olamine restores the protein levels of UROIIIS and its activity [5]. Considering that CEP is an ultra-rare disease, ciclopirox olamine was granted an orphan drug designation for the treatment of CEP by the US Food and Drug Administration (DRU-2018-6297, May 2018) and the European Medicines Agency (EMA/OD/186/17, January 2018) [6].

ATL-001 is a new formulation of ciclopirox olamine for oral administration, containing alginate and tocofersolan as excipients. The proposed indication for ATL-001 is the treatment of CEP.

The term investigational medicinal product (IMP) is used throughout the protocol to describe products received by the subjects as per the protocol design. In this study, five different ATL-001 doses will be tested along with their matching placebos. Thus, all of them are named as IMP in this protocol.

6.2.1 Summary of Non-Clinical Findings

6.2.1.1 Pre-Clinical Safety Data

Preclinical data of ciclopirox olamine have not shown prohibitive findings with respect to reproduction, toxicology, mutagenicity, carcinogenicity or phototoxicity.

Date: 13 December 2023

Sponsor: Atlas Molecular Pharma S.L. Study Code: ATL001-PI-CEP

NCT No.: 05647343

A dermal carcinogenic study in mice of 1% and 5% ciclopirox olamine formulated in polyethylene glycol 400 applied to the intact skin, twice a week, for one year, followed by a six-month follow-up period was conducted. No tumors were observed in any mice at the application site. Overall incidence of neoplasms was similar among the treated and control groups. Moreover, there is no evidence that ciclopirox olamine is carcinogenic following a subcutaneous or oral administration to a number of animal species.

Ciclopirox olamine did not cause chromosomal damage or gene mutation in two mammalian assays or in several bacterial mutagen assays. In a battery of *in vitro* genotoxicity assays with ciclopirox free acid, one assay was weakly positive. Evidence of *in vitro* and *in vivo* assessments suggest that ciclopirox does not present a genotoxic hazard to humans.

Reproductive studies in mice, rats, rabbits and monkeys, at doses of ciclopirox olamine 10 times that of a topical human dose, revealed no significant evidence of impaired fertility or harm to the fetus. There is evidence that ciclopirox olamine crosses the placental barrier in animals.

6.2.1.2 Pharmacodynamic Effects

The effect of ciclopirox olamine on the activity of UROIIIS was demonstrated in cell-based and murine models of CEP. Ciclopirox targeted the enzyme at an allosteric site and did not affect its catalytic role. The drug restored enzymatic activity *in vitro* and *ex vivo* and was able to alleviate most clinical signs of CEP at subtoxic concentrations. Ciclopirox significantly reduced the levels of the toxic porphyrins, particularly uroporphyrin I and coproporphyrin I, in urine, red blood cells, and liver. Furthermore, it reduced splenomegaly, which is considered an indirect measure of reduction in circulating porphyrins [5,6].

6.2.1.3 Pharmacokinetic Properties

The pharmacokinetics (PK) of ciclopirox olamine was initially described during its development as an antifungal agent. Several studies were performed with oral administration, for instance, at a dose of 1 mg ciclopirox-14C-olamine/kg to rats, or in doses between 5-15 mg/kg to dogs. The results indicate that the compound is rapidly eliminated from blood (3–8 h). Most of the compound is renally excreted either unchanged or as glucuronide.

6.2.2 Summary of Clinical Findings

This is a first-in human study designed to assess the safety, tolerability, and PK of oral doses of ATL-001 in healthy adult volunteers, and thus, there is no available clinical research data to date on the IMP.

Nevertheless, other formulations of ciclopirox olamine have been previously orally administered to humans. A Phase I study assessed the tolerability and biologic activity of oral ciclopirox olamine in subjects with relapsed or refractory hematologic malignancy (NCT00990587). The drug was rapidly absorbed and cleared with a short half-life. Ciclopirox had a $t_{1/2}$ of less than 6 hours after both single and repeated administration. Despite the short apparent elimination $t_{1/2}$, the ciclopirox C_{max} values obtained following 80 mg/m² ciclopirox olamine once or four times daily exceeded 1 μ M. Plasma concentrations of an inactive ciclopirox glucuronide metabolite were greater than those of ciclopirox. Grade 3 gastrointestinal dose-limiting toxicities (DLTs) and bowel inflammation were observed in 3 out of the 4 subjects in the cohort receiving 80 mg/m² four times daily. No DLT was observed at 40 mg/m² once daily [7].

6.3 Study Rationale

Non-clinical studies have demonstrated the medical plausibility of ciclopirox for the treatment of CEP, a very rare inherited metabolic disorder resulting from a deficient activity of UROIIIS. This drug acts as a pharmacological chaperone targeting UROIIIS and helps to restore its protein levels and activity.

Despite ciclopirox olamine is active at subtoxic concentrations and it has a fast turnover, acute gastrointestinal toxicity was observed due to the precipitation in the stomach of the active compound and subsequent accumulation in the intestine.

ATL-001 is a new oral formulation of ciclopirox olamine, including alginate and tocofersolan, currently under development for the treatment of subjects with CEP. This new oral formulation was developed

Version: 4.0

Date: 13 December 2023

Sponsor: Atlas Molecular Pharma S.L. Study Code: ATL001-PI-CEP

NCT No.: 05647343

to improve the local tolerance of ciclopirox olamine, which otherwise induces dose-dependent gastrointestinal toxicity.

The present randomized, placebo-controlled, dose escalation, Phase I study aims to investigate the safety, tolerability and PK of ATL-001 at five different dose levels in healthy subjects.

The results of this study are intended to be used to identify appropriate and well tolerated doses of ATL-001 to be used in further studies.

6.4 Rationale for dose selection

The suggested selection of doses is based on the preclinical efficacy, safety and PK data. Efficacy studies in CEP mice suggest activity (defined as reduction of the circulating porphyrin levels in blood) at doses of 2,03 mg/kg (Human Equivalent Dose, HED). Importantly, efficacy is dose dependent. Moreover, PK and non-regulated toxicity studies in rodents (mice and rats) demonstrate that ATL formulation is safe at doses below 18 mg/kg in HED. These studies are further confirmed by a toxicity study in dog under Good Laboratory Practice (GLP-compliant) and further toxicity studies in rat, both at 9.2 mg/kg in HED. In any of these studies gastrointestinal toxicity or any adverse effect were observed. Nonetheless, taking into account that in a previous clinical experience, administration of ciclopirox olamine at 2.2 mg/kg four times daily in patients with hematological malignancies caused grade 3 gastrointestinal dose-limiting toxicities and bowel inflammation, we decided to start with a dose of 0.2 mg/kg, 10-fold lower than that causing toxicity in humans. Altogether, we propose testing 0.2, 0.5, 1, 2 and 4 mg/kg in the current phase trial. A treatment duration of 5 days was selected based on GLP-compliant Toxicokinetic study performed in dogs and considering that this time will suffice to observe the lack of gastrointestinal toxicity. In addition, the lack of toxicity (including gastrointestinal toxicity) observed in another GLP-compliant study, where dogs were daily administered with ATL-001 by the oral route during 28 days at 7.2 mg/kg (corresponding to a HED of 4 mg/kg), supports the safety of the dose of 4 mg/kg proposed for the 5th arm.

6.5 Potential Risks and Benefits

An analysis of potential risks for subjects participating in this study has been made. Identified risks and actions taken for their mitigation are summarized in Table 2.

Table 2. Identified Risk and Risk Minimization Actions

Identified Risk	Risk Minimization Actions
Gastrointestinal toxicity	Staggered approach to enrollment. The escalation to the next dose cohort should only occur after the safety and tolerability data from the current cohort is reviewed and deemed acceptable. Inclusion of DLTs and DSMB. Vital signs and physical examination monitoring.

DLT, dose-limiting toxicity; DSMB, Data and Safety Monitoring Board.

Risks and Benefits - Conclusion

The Sponsor considers the risk of serious adverse reactions to the IMP to be low, given the preventive actions taken and data from supporting animal studies. In conclusion, the named Sponsor believes the potential benefits of study participation outweigh the potential risks.

Version: 4.0

Date: 13 December 2023

Sponsor: Atlas Molecular Pharma S.L. Study Code: ATL001-PI-CEP NCT No.: 05647343

7. STUDY OBJECTIVES AND ENDPOINTS

Objective	Endpoint
Primary	
The primary objective of the study is to investigate the safety and tolerability of ATL-001 in healthy subjects	Incidence of adverse events (AEs) and of clinically relevant changes in vital signs values, electrocardiogram (ECG) data, physical examination and laboratory safety data for five different doses of ATL-001
Secondary	
To determine the PK of ATL-001 in healthy subjects	Derived pharmacokinetic parameters for ATL-001 including area under the plasma drug concentration versus time curve (AUC _(0-last) , AUC ₍₀₋₁₂₎ , AUC ₍₀₋₂₄₎), maximum observed plasma drug concentration (C _{max}), time to maximum observed plasma drug concentration (t _{max}), apparent terminal half-life (t _{1/2}), apparent total body clearance (CL/F) and apparent volume of distribution (Vz/F), as appropriate

Version: 4.0

Date: 13 December 2023

Sponsor: Atlas Molecular Pharma S.L. Study Code: ATL001-PI-CEP

NCT No.: 05647343

8. INVESTIGATIONAL PLAN

8.1 Study Design and Plan-Description

This is a Phase I, double-blind, randomized, parallel-design, placebo-controlled, and dose escalation study to investigate the safety and PK of ATL-001 (ciclopirox olamine) in healthy subjects.

The study will consist of five sequentially recruited cohorts of 8 subjects each, resulting in up to 40 randomized subjects. Subjects will not be allowed to participate in more than one cohort.

Five different ATL-001 doses will be tested along with their matching placebos: ATL-001 0.2 mg/kg, ATL-001 0.5 mg/kg, ATL-001 1 mg/kg, ATL-001 2 mg/kg and ATL-001 4 mg/kg (see Section 10.1.1). All of them are named as IMP in this protocol. On the morning of Day 1 to Day 5, each subject will receive a single oral dose of ATL-001 or placebo (i.e., total of 5 administrations of IMP) administered under fasting conditions (overnight fast; at least 10 hours) following the instructions below (Table 3).

The day of the first administration of the IMP will be considered Day 1 of the study.

Table 3. Study Cohorts Treatment Plan

Cohort	Investigational medicinal product	Route	Administration Days
1	ATL-001 0.2 mg/kg / Placebo	Oral	1, 2, 3, 4, 5
2	ATL-001 0.5 mg/kg / Placebo	Oral	1, 2, 3, 4, 5
3	ATL-001 1 mg/kg / Placebo	Oral	1, 2, 3, 4, 5
4	ATL-001 2 mg/kg / Placebo	Oral	1, 2, 3, 4, 5
5	ATL-001 4 mg/kg / Placebo	Oral	1, 2, 3, 4, 5

In order to maintain the double-blind study, the administration of the IMP must occur individually and separately, and in the absence of the physician responsible for the study. This is because the reaction after its administration could be easily distinguishable between placebo and ATL-001.

Given that the inclusion criteria established in Section 9.2 determine the selection of subjects with a minimum weight of 50 kg and a maximum of 100 kg, the volumes of IMP to be administered depending on the dosage are shown in Table 4. The corresponding volume in each case will be extracted using an FDA-recommended syringe (3-Piece Syringe Complies with international standards [ISO 7886-1]).

Table 4. Volumes of IMP to be Administered and the Corresponding Syringes

Cohort	Volume	Syringe
ATL-001 0.2 mg/kg / Placebo	From 0.5 mL to 1 mL	3 mL (scale - 0.1)
ATL-001 0.5 mg/kg / Placebo	From 1.5 mL to 3 mL	3 mL (scale - 0.1)
ATL-001 1 mg/kg / Placebo	From 2.5 mL to 5 mL	10 mL (scale – 0.2)
ATL-001 2 mg/kg / Placebo	From 5 mL to 10 mL	10 mL (scale – 0.2)
ATL-001 4 mg/kg / Placebo	From 10 mL to 20 mL	10 mL (scale - 0.2)

Date: 13 December 2023

Sponsor: Atlas Molecular Pharma S.L. Study Code: ATL001-PI-CEP

NCT No.: 05647343

The volume to be administered will be extracted from the IMP container and will be deposited in a glass containing approximately 50-100 ml of water and to which 2-4 tablespoons of sugar have been added. The IMP will be stirred with a spoon and drunk in one gulp, if possible.

For each cohort, subjects will be screened up to 30 days prior to the Baseline visit. All eligible subjects will be admitted to the study site on Day 1 (Baseline), for baseline assessments and to confirm their eligibility. They will remain domiciled until discharged on Day 2, after completion of the assessments and after receiving the IMP. All screening safety evaluation results must be available prior to dosing. Subjects will be randomized immediately prior to Day 1 IMP administration. At Day 5, subjects will be admitted again to the study site, where they will remain domiciled until discharged on Day 6 after completion of the assessments. Subjects will return to the study site 3 days after their last IMP dose and 30 days after last IMP dose to undergo safety follow-up evaluations.

For each cohort, the subjects will be randomized to receive ATL-001 (6 subjects/cohort) or to receive placebo (2 subjects/cohort). Each cohort will be sub-divided into 2 sub-cohorts (Figure 1):

- The first sub-cohort will have 2 sentinel subjects: one will be randomized to receive ATL-001 and one to receive placebo. Once these subjects complete their follow-up visit 1 (FU-V1) (3 days after the last IMP dose), the Sponsor and Principal Investigator (PI) will review all the available safety and tolerability data before deciding the inclusion of the remaining 6 subjects in the second sub-cohort.
- The second sub-cohort will include 6 additional subjects simultaneously: 5 randomized subjects to receive ATL-001 and 1 to receive placebo. Upon availability of the FU-V1 (3 days after the last IMP dose) data of all subjects, the Data and Safety Monitoring Board (DSMB) will review all available safety, tolerability, and will issue a recommendation for the next cohort to start (Section 8.1.1). Only then the study may proceed with the next cohort for treatment administration after Sponsor decision. The same procedure will be followed for each subsequent cohort.

Depending on safety and tolerability data, the dose and administration schedule of ATL-001 might be recommended by the DSMB and changed after approval and authorization of the Sponsor (Section 8.1.1).

Additionally, the timing and number of safety assessments may be modified during the study after DSMB recommendation based on the results of emerging data (Section 8.1.1).

Any DSMB recommendation that would lead to a substantial amendment of the study protocol will be submitted to the Institutional Review Board (IRB) and Regulatory Authority (RA).

Version: 4.0

Date: 13 December 2023

Sponsor: Atlas Molecular Pharma S.L.

Study Code: ATL001-PI-CEP

NCT No.: 05647343

[figure not shown]

Figure 1. Overall Study Design

PI, Principal Investigator; R, Randomization.

8.1.1 Data and Safety Monitoring Board Evaluation

The DSMB will issue recommendations regarding proceeding to each subsequent cohort based on all available safety, tolerability from all prior cohorts. The stopping rules described in Section 8.1.2 and the DLTs described in Section 8.1.3 will be considered.

Additionally, if the study level stopping rules described in Section 8.1.2 are met, the DSMB will automatically meet and issue a recommendation. The final decision on these actions will be taken by the Sponsor. The DSMB may meet additional times at the request of the PI or the Sponsor.

The DSMB may issue the following recommendations:

- To recommend the dosing start for the next cohort
- To change the dose for the next cohort*
- To repeat a dose that has been previously studied
- To change the administration schedule
- To add or change the timing of safety and/or PK assessments
- To recommend to the Sponsor that dosing should be stopped

^A After sentinel subjects complete FU-V1 (3 days after the last IMP dose)

^B Upon availability of the FU-V1 (3 days after the last IMP dose) data of all the cohort subjects. Final decision will be taken by the Sponsor based on DSMB recommendation

^{*}The DSMB proposed ATL-001 dose for a given cohort should not be superior to 8.1 mg/kg (see Appendix 1).

Date: 13 December 2023

Sponsor: Atlas Molecular Pharma S.L. Study Code: ATL001-PI-CEP

NCT No.: 05647343

A DSMB charter will be produced by the Sponsor and will contain the following details:

- Committee members and requirements for quorum
- Data review requirements
- Process for informing the IRB and RA of any safety concerns, if appropriate
- Process for requesting additional pertinent information from the investigators
- Process for informing the investigators (and IRB/RA, if appropriate) of any decisions derived from the recommendations of the DSMB

8.1.2 Study-Level Stopping Rules

In case of any occurrence of one of the following criteria in one of the cohorts, the IMP administration will be temporarily stopped and the DSMB will meet to review the safety and tolerability data and issue a recommendation:

- 1 serious AE (SAE) in one subject that is considered to be at least possibly related to the IMP
- ≥2 subjects of one cohort (or 1 out of 2 sentinel subjects) reporting grade ≥2 or higher AEs that are considered to be at least possibly related to the IMP, regardless of attribution or relatedness to further enhance safety in this healthy volunteer study

If, after stopping the study, the Sponsor deem it appropriate to restart the study following a safety review by the DSMB, this will be done following approval of a substantial protocol amendment.

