8.1.3 Dose-Limiting Toxicities

In case of any occurrence of one of the following criteria in one of the cohorts, no further dose escalation will be applied in subsequent cohorts:

- ≥ 1 subject of one cohort reporting grade ≥2 AEs up to FU-V1 (3 days after the last IMP dose)
- Corrected QT interval by Fredericia (QTcF) ≥500 ms and/or an increase of QTcF from baseline of ≥ 60 ms, confirmed by repeated ECGs, in at least 1 subject up to FU-V1 (3 days after the last IMP dose)

NOTE: Only toxicities with a clear-cut alternative explanation will be deemed non-DLT.

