factors is unlikely. The clinical event, including an abnormal laboratory test result, occurs within a reasonable time after administration of the study treatment, is unlikely to be attributed to concurrent disease or other drugs or chemicals, and follows a clinically reasonable response on withdrawal (dechallenge). Rechallenge information is not required to fulfill this definition.

Possible: There is some evidence to suggest a causal relationship (e.g., the event

occurred within a reasonable time after administration of the study treatment). However, other factors may have contributed to the event (e.g., the subject's

clinical condition, other concomitant events).

Not Related to the Study Treatment

Unlikely: A clinical event, including an abnormal laboratory test result, whose temporal

relationship to study treatment administration makes a causal relationship improbable (e.g., the event did not occur within a reasonable time after administration of the study treatment) and in which other drugs or chemicals or underlying disease provides plausible explanations (e.g., the subject's

clinical condition, other concomitant treatments).

Not Related: The AE is completely independent of study treatment administration, and/or

evidence exists that the event is definitely related to another etiology. There

must be an alternative, definitive etiology documented by the clinician.

Follow-up of Subjects after Adverse Events

Any AE that is ongoing when the subject is withdrawn from the study should be followed up until the AE is resolved or the Investigator decides that the AE is stable and needs no further follow-up. The date when the Investigator considers one of these outcomes to have occurred for the last ongoing AE for a subject will be considered the last visit for this subject, and the outcome should be recorded in the eCRF.

Abnormal Laboratory Values/Vital Signs

The reporting of abnormalities as both laboratory/vital signs findings and AEs should be avoided.

An asymptomatic abnormal laboratory/vital sign finding should only be reported as an AE if it is clinically significant, if it fulfils the criteria for a SAE or if it causes the subject to discontinue the study.

If an abnormal laboratory/vital sign value is associated with clinical signs and symptoms, the sign/symptom should be reported as an AE and the associated laboratory/vital sign result should be considered additional information.

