13.4 Interim Analysis

The safety and tolerability data will be reviewed for each cohort during the DSMB meetings (see Section 8.1).

In addition, a Statistical Analysis has been conducted after completing Cohort 4 (2 mg/kg) and before enrolling subjects in Cohort 5 (4 mg/kg).

Date: 13 December 2023

Sponsor: Atlas Molecular Pharma S.L. Study Code: ATL001-PI-CEP Version: 4.0

NCT No.: 05647343

14. RESULTS FROM THE ANALYSIS REGARDING SAFETY AND EFFICACY OF COHORTS 1 TO 4 ARE AVAILABLE IN SECTION 6.3 OF THE IB.INVESTIGATOR/SPONSOR **RESPONSIBILITIES**

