5.4.3.2 Adverse events

All AEs (TEAEs and non TEAEs) will be coded to System Organ Class (SOC) and Preferred Term (PT) using the MedDRA dictionary v25.1. or later.

The NCI-CTCAE version 5.0 or higher when available will be used to assess the severity grade of TEAEs.

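### The second stopping criterion in Protocol 8.1.2 both requires relatedness and disregards it, so it gives no single answer for grade ≥2 AEs judged Unlikely or Not Related

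*Protocol*

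**What the plan says.** Protocol 8.1.2 lists two events that pause IMP administration and call the DSMB. The first is a single SAE with at least a possible relationship to the IMP. The second has the threshold "≥2 subjects of one cohort (or 1 out of 2 sentinel subjects) reporting grade ≥2 or higher AEs", and those AEs are then described as "considered to be at least possibly related to the IMP, regardless of attribution or relatedness to further enhance safety in this healthy volunteer study".

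Three steps follow from meeting a criterion:

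- Dosing is paused.
- Under Protocol 8.1.1, "if the study level stopping rules described in Section 8.1.2 are met, the DSMB will automatically meet and issue a recommendation".
- If the sponsor wants to restart after the study has been stopped, 8.1.2 says "this will be done following approval of a substantial protocol amendment".

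Protocol 12.2 has five causality categories. Definitely Related, Probable and Possible form the related group. Unlikely and Not Related form the unrelated group, and Not Related is defined by "The AE is completely independent of study treatment administration".

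**The concern.** A stopping rule has to give one answer for every event that can occur, because staff apply it under time pressure and without discretion. This bullet gives two answers for a defined class of AEs. Suppose one sentinel has a single grade 2 AE judged Not Related. One clause halts dosing and the other does not.

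Site staff could therefore continue dosing healthy volunteers where half of the sentence requires a halt. Equally, they could stop and face an amendment where the other half requires neither.

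The matter is most acute in Cohort 5 (4 mg/kg), the highest and last planned dose. Protocol 13.4 shows that Cohort 4 was complete before Cohort 5 enrolled. The DLT rule in 8.1.3 acts only on later cohorts ("no further dose escalation will be applied in subsequent cohorts"), so it offers little backup there.

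**Working it through.** **Step 1. Apply each clause to the causality scale in Protocol 12.2.**

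| Investigator's causality | Relatedness clause | Disregard-attribution clause |
|---|---|---|
| Definitely Related, Probable, Possible | counts | counts |
| Unlikely, Not Related | does not count | counts |

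The conflict is confined to the second row. It bites when the related AEs do not already meet the threshold.

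**Step 2. Look for a resolving provision.**

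- Protocol 8.1.1 acts only if the 8.1.2 rules are met, so it inherits the ambiguity.
- Protocol 8.1.3 has a lower count (one subject with a grade ≥2 AE) and exempts events with an evident other cause. It governs escalation, not dosing in the current cohort.
- SAP 5.4.7 describes DSMB review without restating any criteria.
- The change table in Protocol 1.1 records only that the stopping criteria were revised in Version 2.0 after FDA suggestions.

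None of these decides which clause applies.

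**Step 3. Illustrate the size.** The plan states no stopping probability, so there is no figure to reproduce.

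Inputs from Protocol 8.1 and 8.1.2: a cohort of 8, made up of 2 sentinels and 6 others. The trigger is at least 1 of 2 sentinels, or at least 2 of 8.

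Assumed inputs: the per-subject probability *a* of a grade ≥2 AE from any cause, the share *r* of those judged related, and independence between subjects.

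The rule does not fire only if no sentinel has a qualifying AE and at most one of the other six does:

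P(trigger) = 1 − (1 − p)² × [(1 − p)⁶ + 6p(1 − p)⁵]

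Here p = a if all AEs count, and p = a × r if only related AEs count.

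With a = 0.10 and r = 0.30:

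- Related only, p = 0.03: 1 − 0.9409 × 0.98754 = 0.0708.
- All AEs, p = 0.10: 1 − 0.81 × 0.88574 = 0.2826.
- Gap: 0.2826 − 0.0708, about 0.212, which is 75% of the any-cause triggers.
- Sentinel pair alone, 1 − (1 − p)²: 0.0591 against 0.1900.

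A simulation of 1,000,000 cohorts gave 0.0704 and 0.2824.

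| a | r | Related only | All AEs | Gap (points) | Gap as share of any-cause triggers |
|---|---|---|---|---|---|
| 5% | 30% | 3.3% | 12.7% | 9.4 | 74% |
| 5% | 50% | 5.8% | 12.7% | 6.9 | 55% |
| 10% | 30% | 7.1% | 28.3% | 21.2 | 75% |
| 10% | 50% | 12.7% | 28.3% | 15.5 | 55% |
| 15% | 30% | 11.3% | 43.9% | 32.6 | 74% |
| 15% | 50% | 20.3% | 43.9% | 23.6 | 54% |

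**The case against.** The best counter-argument is that the intent can be inferred. Only the disregard-attribution clause carries a stated purpose, and the SAE bullet has the relatedness condition without it. The second bullet therefore looks like a deliberate widening with old wording left in. That is probably right, and it guides the fix. But a mandatory halt should not depend on the reader deciding which half of a sentence was meant to be deleted.

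Second, the disputed AEs are those with another likely cause, and other controls remain:

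- the stop for a related SAE;
- Sponsor and PI review of the sentinels before the other six enter;
- DSMB review of each cohort, and extra DSMB meetings on request;
- the PI's right to stop the study.

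This stands. It limits the gap to the automatic pause and what follows from it.

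Third, 8.1.2 speaks of pausing administration and then of restarting after stopping the study. One could argue that the amendment is not needed after every pause. The section describes no other kind of stop, so the natural reading links the two, but the caution is fair.

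Fourth, the probabilities describe triggers, not interrupted doses. The six later subjects start together and dose for five days, so an AE arising in them after Day 5 leaves no dosing in that cohort to halt. This also stands. The figures overstate actual dosing interruptions, though the duty to convene the DSMB would still turn on the reading.

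Finally, the DSMB charter is not among the documents, so day-to-day practice cannot be judged. A charter cannot override the protocol.

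**Conclusion.** The concern holds. As written, the second criterion gives opposite instructions for grade ≥2 AEs judged Unlikely or Not Related, and nothing in the protocol or SAP resolves them. That conclusion rests on the text alone.

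The size is illustrative. It depends on assumed AE rates, assumed related shares, independent subjects and a common rate. Over the range examined, the choice of clause moves the per-cohort trigger probability by about 7 to 33 percentage points, and 54–75% of any-cause triggers depend on it. The 10%/30% example lies at the top of that share range; with half of the AEs judged related, the share is about 55%. The defect is narrow, but it sits in a mandatory safety rule and needs correcting.

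**What to change.** Keep one attribution rule. Given the stated purpose, delete the condition requiring at least a possible relationship to the IMP. The bullet then keeps its threshold of two subjects in a cohort or one of two sentinels, and counts any grade ≥2 AE whatever its attribution. The sponsor should confirm this intent and put identical wording in the DSMB charter.

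In the same edit, say that grade means NCI-CTCAE grade. Protocol 12.1.1 already uses that scale, and SAP 5.4.3.2 says it "will be used to assess the severity grade of TEAEs", but Protocol 12.2 also describes severity as mild, moderate or severe.

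The change needs a protocol amendment of wording and a charter update, with no added subjects or assessments. The operational price of the any-cause rule is more frequent stops: under the 10%/30% assumption, about 28% of cohorts instead of 7%. On the natural reading of 8.1.2, each would need a substantial amendment before restart. If the sponsor finds that too heavy, the alternative is to delete the disregard-attribution clause openly and accept the narrower rule.
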